8.3.3 Safety Set

The Safety Set will comprise all subjects in the FAS who received at least one dose or partial dose of Study Vaccine and have provided any evaluable follow-up safety data. The safety set will be used to produce summaries and listings of all safety data.

8.3.4 Evaluable Set – Immunogenicity Analysis

The Evaluable Set for immunogenicity analyses will comprise all subjects in the FAS who:

- receive vaccine on Day 1
- provide serology specimens which yield valid serology assay results from both Day 1 and Day 29 (Previously vaccinated subjects) or Day 1 and Day 57 (Not previously vaccinated subjects)
- do not experience a laboratory-confirmed influenza illness between Day 1, Day 29, and Day 57
- do not receive any prohibited medication during the study that is medically assessed to potentially impact immunogenicity results

8.3.5 Per Protocol Set

The Per-Protocol Set (PPS) will comprise all subjects in the Evaluable Set who do not have any protocol deviations that are medically assessed as potentially impacting on immunogenicity results.

The Per Protocol Set will be the primary population of interest for the primary/secondary immunogenicity analysis and a supporting analysis will be performed using the Evaluable Set. Membership of the PPS will be determined prior to unblinding the study.

Duplicate tables of primary and secondary immunogenicity analyses may also be produced based on the Evaluable population if there is >1% difference in the total number of subjects between the Per-Protocol Population and the Evaluable Population. The decision to produce tables based on the Evaluable Population will be made by Seqirus after population sets are finalized and prior to unblinding.

Examples for subjects excluded due to other reasons than protocol deviations are subjects who withdrew informed consent.

In case of misrandomization with regard to treatment arm, the subject is excluded from the PPS.

If a subject is unblinded during the study, except for SUSAR, he/she will be excluded from the PPS.

8.3.6 Subgroups

The immunogenicity analysis will be performed by stratifying for the following subgroups:

- Subjects with a prevaccination HAI titer < 1:10 and prevaccination HAI titer \geq 1:10
- Subjects with a prevaccination MN titer < LLOQ and prevaccination MN titer \geq LLOQ
- Subjects with and without recent seasonal influenza vaccine (defined as influenza vaccine within the past 12 months).
- Subjects "previously vaccinated" and "not previously vaccinated."
- Subjects will be additionally analyzed by age, center, gender, race and ethnicity.

Safety analyses will also be performed by age groups and time periods as detailed in the SAP.

8.3.7 Protocol Deviations

A protocol deviation is any change, divergence, or departure from the study design or procedures of a study protocol. A protocol deviation may be a reason to remove data from an analysis set at the time of analysis. Clinical study report (CSR)-reportable (major) protocol deviations will be defined as exclusionary from the analysis according to protocol objectives and endpoints, which will be specified in the Protocol Deviation Specifications to this study protocol. In some cases, exclusion of data may be due to a reason other than a protocol deviation, e.g. early termination.

8.4 Statistical Analysis Plan

A complete description of the statistical analyses and methods will be available in the Statistical Analysis Plan (SAP), which will be finalized prior to unblinding.

8.4.1 Analysis of Demographic and Baseline Characteristics

Descriptive statistics (mean, standard deviation, median, minimum and maximum) for age, height, weight, BMI, and comorbidity score at enrollment will be calculated overall and by vaccine groups.

Distributions of subjects by sex, ethnic origin (race, ethnicity), and previous vaccination status will be summarized overall, and by vaccine group.

8.4.1.1 Concomitant Medications

Use of concomitant medication will be presented by treatment, age cohort, therapeutic area, and preferred drug name.

Concomitant medications are all medications taken during the study period, including those started before but ongoing at vaccination.

If a start date for a medication is partially or fully missing, and it is unclear as to whether the medication is prior or concomitant, it will be assumed that it is concomitant.

Medications will be coded using the WHO Drug dictionary.

8.4.2 Analysis of Primary Objective(s)

8.4.2.1 Analysis of Primary Safety Objective(s)

Not applicable.

8.4.2.1.1 Analysis of Extent of Exposure

Not applicable.

8.4.2.1.2 Analysis of Solicited Local, Systemic and Other Adverse Events

Not applicable.

8.4.2.1.3 Analysis of Unsolicited Adverse Events

Not applicable.

8.4.2.1.4 Analysis of Safety Laboratory Values

Not applicable.

8.4.2.2 Analysis of Primary Efficacy Objective(s)

8.4.2.2.1 Statistical Hypothesis

Not applicable.

8.4.2.2.2 Analysis Sets

Not applicable.

8.4.2.2.3 Statistical Methods

Not applicable.

8.4.2.3 Analysis of Primary Immunogenicity Objective(s)

The primary immunogenicity objective is:

1. To demonstrate that vaccination with QIVc elicits an immune response that is not inferior to that of an US-licensed QIV containing the recommended strains for the season, in subjects 6 months through 47 months of age, as measured by hemagglutination inhibition (HAI) assay for A/H1N1, B/Yamagata and B/Victoria strains and by microneutralization (MN) assay for A/H3N2 strain, using cell-derived target viruses.

8.4.2.3.1 Statistical Hypothesis

Noninferiority of QIVc to US-licensed QIV

The noninferiority of QIVc compared to the US-licensed QIV will be assessed by the 8 co-primary endpoints of GMT and SCR for the A/H1N1, A/H3N2 and the B strains. Definitions for noninferiority based on endpoints measured by HAI are derived from the FDA Guidance on seasonal inactivated influenza vaccines (*Guidance for Industry Clinical Data Needed to Support Licensure of Seasonal Inactivated Influenza Vaccines 2007*). A modified definition will be applied to assessment of the endpoint based on the MN assay. Specifically, Seqirus QIVc will be considered to be noninferior to the US-licensed QIV if, for each of the four strains, the following statistical criteria are met:

A/H1N1 and B strains:

- The upper bound of the two-sided 95% confidence interval (CI) on the ratio of the HAI GMTs does not exceed 1.5. The HAI GMT ratio will be calculated as HAI GMT US-licensed comparator QIV *divided* by HAI GMT QIVc
- The upper bound of the two-sided 95% CI on the difference between the HAI SCRs does not exceed 10%. The difference in HAI SCRs will be calculated as HAI Seroconversion US-licensed comparator QIV *minus* HAI Seroconversion QIVc. The 95% CI will be computed based on the binomial distribution

A/H3N2 strain only:

- The upper bound of the two-sided 95% confidence interval (CI) on the ratio of the MN GMTs does not exceed 1.5. The MN GMT ratio will be calculated as MN GMT US-licensed comparator QIV *divided* by MN GMT QIVc.
- The upper bound of the two-sided 95% CI on the difference between the MN SCRs does not exceed 10%. The difference in MN SCRs will be calculated as MN Seroconversion US-licensed comparator QIV *minus* MN Seroconversion QIVc. The 95% CI will be computed based on the binomial distribution.

In mathematical notation the statistical hypotheses to be tested for the primary noninferiority immunogenicity analysis corresponds to:

- $H_0: R_i > 1.5$, for any strain
- $H_a: R_i \leq 1.5$, for any strain, and
- $H_0: D_i > 10$, for any strain
- $H_a: D_i \leq 10$, for all strain

where R_i is any of the 4 strain-specific post immunogenicity dose GMT ratios:

- $(\text{US-licensed comparator QIV}) / (\text{QIVc})$ for B/Yamagata strain
- $(\text{US-licensed comparator QIV}) / (\text{QIVc})$ for B/Victoria strain
- $(\text{US-licensed comparator QIV}) / (\text{QIVc})$ for A/H1N1 strain
- $(\text{US-licensed comparator QIV}) / (\text{QIVc})$ for A/H3N2 strain

and D_i is the 4 strain-specific post-dose SCR difference, namely

- $(\text{US-licensed comparator QIV}) - (\text{QIVc})$ for B/Yamagata strain
- $(\text{US-licensed comparator QIV}) - (\text{QIVc})$ for B/Victoria strain
- $(\text{US-licensed comparator QIV}) - (\text{QIVc})$ for A/H1N1 strain
- $(\text{US-licensed comparator QIV}) - (\text{QIVc})$ for A/H3N2 strain

No adjustment will be made for multiple comparisons.

8.4.2.3.2 Analysis Sets

The Per Protocol Set will be used for the primary immunogenicity analysis and a supporting analysis will be performed using the Evaluable Set, as noted in [Section 8.3.4](#). **Evaluable Set – Immunogenicity Analysis.** Duplicate tables of primary and secondary immunogenicity analyses may also be produced based on the Evaluable population if there is >1% difference in the total number of subjects between the Per-Protocol Population and the Evaluable Population.

8.4.2.3.3 Statistical Methods

All statistical analyses for HAI (or MN) titers will be performed on the logarithmically transformed (base 10) values. Individual HAI titers below the detection limit (<10) will be set to half of that limit (5). Individual MN titers below the lower limit of quantification (LLOQ), will be set to half of that limit (1/2* LLOQ).

Co-primary immunogenicity endpoints of GMT and SCR for each virus strain contained in the vaccine will be assessed in subjects 6 Months through 47 Months of Age overall.

Primary analysis will be performed in subjects 6 Months through 47 Months of Age for the Per-Protocol Set. The difference in SCRs will be presented with exact 95% (CIs). Each of the four strains will be analyzed separately.

To determine the GMT ratio (adjusted analysis) a general linear model (GLM) will be fitted on log transformed (base ten) postvaccination HAI (or MN) titers as the outcome variable and terms for covariates: vaccine treatment, prevaccination HAI (or MN) titer, age stratum, gender, vaccination history, age-by-vaccine interaction and study site. The complete set of covariates that may be used in the model to calculate the adjusted GMT will be specified in the SAP.

Potential covariate interaction effects will also be examined in the fit of the GLM. From the model, an adjusted difference in least square means (on the log scale) will be produced with 95% confidence limits. The estimated difference and the confidence limits will be back transformed to obtain an *adjusted GMT ratio* with 95% confidence limits. Each of the four strains will be analyzed separately. The adjusted GMT ratio will be the result for which the noninferiority assessment of the HAI (or MN) GMT co-primary endpoint will be based on.

The statistical models might be reduced in case they fail to converge. Further details will be provided in the Statistical Analysis Plan.

The complete set of covariates that may be used in the model to calculate the adjusted GMT ratio will include treatment group (2 treatments), age sub-group, gender (male or female), influenza vaccination received prior year (Y or N), prevaccination mean GMT titer (value) and investigator site (site identifier)

The GLM specification is:

*Adjusted Analysis GMT Model: Log-transformed Postvaccination HAI (or MN) Titer = Vaccine + Age Strata + Gender + Vaccination History [y/n] + Log-transformed Prevaccination HAI (or MN) Titer + Site + Age Strata*Vaccine.*

For any strain, the interaction term *Age Strata*Vaccine* will be removed from the fit of the model if it is assessed to be not significant.

The measure of the *unadjusted* GMT ratio based on postvaccination GMT only will also be presented.

Binary data (ie, percentages of subjects with seroconversion and with titer $\geq 1:40$) will be summarized for each group using unadjusted estimates and will be reported together with two-sided exact 95% CIs. No multiplicity adjustment to the CI levels will be implemented.

If all 8 co-primary endpoints fulfilled noninferiority criteria then overall noninferiority of QIV compared to the US-licensed comparator QIV was to be concluded.

Handling of Missing Values for Immunogenicity Data

For immunogenicity data, it may be reasonable to consider missing immunogenicity values as missing completely at random (MCAR), ie, not informative. Therefore, the immunogenicity and key secondary analyses will comprise a complete case analysis only, without introducing any bias. Imputation methods will not be used. Further details of the statistical methods will be provided in the SAP.

8.4.3 Analysis of Secondary Objective(s)

8.4.3.1 Analysis of Secondary Safety Objective(s)

8.4.3.1.1 Analysis of Extent of Exposure

The number of subjects actually receiving the vaccinations will be summarized by vaccine group.

8.4.3.1.2 Analysis of Solicited Local, Systemic and Other Adverse Events

All solicited adverse events will be summarized according to defined severity grading scales.

Frequencies and percentages of subjects experiencing each adverse event will be presented for each symptom severity. Summary tables showing the occurrence of any local or systemic adverse event overall and at each time point will also be presented.

Postvaccination solicited adverse events reported for 7 days after each vaccination and will be summarized for the intervals day 1 to 3, day 4 to 7, day 1 to 7 by maximal severity and by vaccine group, excluding the 30-minute measurement, which will be summarized separately. Injection-site erythema, ecchymosis, and induration will be summarized according to categories based on linear measurements: Type I: none (0 mm), any (1 to <10 mm, 10 to 25 mm, 26 to 50 mm, >50 mm); Type II: Grade 0 (<10 mm), any (10 to 25 mm, 26 to 50 mm, >50 mm) (see SAP for further details).

Injection site tenderness and systemic adverse events (except fever) occurring up to 7 days after each vaccination will be summarized according to “mild”, “moderate” or “severe” categorization. For the definition of severity grades see [Section 7.1.3, Evaluation of Adverse Events](#) of the protocol and SAP.

Each solicited local and systemic adverse event will also be further summarized as “none” versus “any.” “Any” will include reactions with a diameter of at least 1 mm.

Implausible measurements (for further definition see SAP) will be left out of the analysis.

Use of antipyretics and analgesics will be summarized by frequency, by type of use (prophylactic versus treatment) and percentage of subjects reporting use.

Body temperature will be summarized by 0.5°C and 1.0°C increments from 36.0°C to ≥40°C and will be broken down by route of measurement and by age cohort.

8.4.3.1.3 Analysis of Unsolicited Adverse Events

This analysis applies to all adverse events occurring during the study, judged either as probably related, possibly related, or not related to vaccination by the investigator, recorded in AE CRF, with a start date on or after the date of first vaccination. AE starting prior to the first vaccination will only be listed.

The original verbatim terms used by investigators to identify AEs in the CRFs will be mapped to preferred terms using the Medical Dictionary for Regulatory Activities (MedDRA) dictionary. The AEs will then be grouped by MedDRA preferred terms into frequency tables according to system organ class (SOC). All reported AEs, as well as AEs judged by the investigator as at least possibly related to study vaccine, will be summarized according to system organ class and preferred term within system organ class. These summaries will be presented by vaccination group and by interval of study observation (Day 1 to Day 29, Day 29 to Day 181 in “previously vaccinated” subjects and Day 1 to Day 57, Day 57 to Day 209 in “not previously vaccinated” subjects). When an AE occurs more than once for a subject, the maximal severity and strongest relationship to the vaccine group will be counted.

Separate summaries will be produced for the following categories:

- SAE
- NOCDs
- Adverse events that are possibly or probably related to vaccine
- Adverse event leading to withdrawal or early termination
- Adverse event resulting in death
- Adverse events leading to a medically-attended visit during the treatment period

Data listings of all adverse events will be provided by subject. In addition, adverse events in the categories above will be provided as listed data.

8.4.3.1.4 Statistical Hypotheses

Not applicable.

8.4.3.1.5 Analysis Sets

Not applicable.

8.4.3.1.6 Statistical Methods

Not applicable.

8.4.3.2 Analysis of Secondary Efficacy Objective(s)

8.4.3.2.1 Statistical Hypothesis

Not applicable.

8.4.3.2.2 Analysis Sets

Not applicable.

8.4.3.2.3 Statistical Methods

Not applicable.

8.4.3.3 Analysis of Secondary Immunogenicity Objective(s)

Characterization of immunogenicity of QIVc

The measures for immunogenicity will be determined by HAI and MN assay for Day 1 and Days 29/57 (depending on influenza vaccination history). HAI will be evaluated in all

subjects, tested against A/H1N1 and both B strains. MN will also be evaluated in all subjects, tested against A/H3N2 strain.

Humoral immune response in terms of HAI antibodies against A/H1N1, B/Victoria and B/Yamagata strains, using cell- and egg-derived target virus:

- GMT by HAI assay at Days 1 and 29/57
- Geometric Mean Ratio (GMR), defined as the fold increase in serum HAI GMTs postvaccination (Day 29/57) compared to prevaccination (Day 1)
- Seropositivity rates (percentages of subjects with HAI titer $\geq 1:10$) at Days 1 and 29/57
- Percentages of subjects with HAI titer $\geq 1:40$ at Days 1 and 29/57
- SCR by HAI assay

Derived variables:

- The GMT ratio (QIV/QIVc) for each strain
- The inter-group difference in the SCRs (QIV minus QIVc) for each strain

Neutralizing antibody titers against A/H3N2 vaccine strains, using cell- and egg-derived target virus:

- GMT by MN assay at Days 1 and 29/57
- GMR, defined as the fold increase in serum MN GMT postvaccination (Day 29/57) compared to prevaccination (Day 1)
- Seropositivity rates (percentages of subjects with MN titer $\geq 1:10$ (LLOQ)) at Days 1 and 29/57
- SCR by MN assay

Derived variables:

- The GMT ratio (QIV/QIVc) for each strain
- The inter-group difference in the SCRs (QIV minus QIVc) for each strain

Neutralizing antibody titers against A/H1N1, B/Victoria and B/Yamagata vaccine strains, in a subset of subjects:

- GMT by MN assay at Days 1 and 29/57
- GMR, defined as the fold increase in serum MN GMT postvaccination (Day 29/57) compared to prevaccination (Day 1)
- Seropositivity rates (percentages of subjects with MN titer $\geq 1:10$ (LLOQ)) at Days 1 and 29/57;
- SCR by MN assay

Derived variables:

- The GMT ratio (QIV/QIVc) for each strain

- The inter-group difference in the SCRs (QIV minus QIVc) for each strain

8.4.3.3.1 Statistical Hypotheses

No statistical testing will be performed for the secondary immunogenicity objectives.

8.4.3.3.2 Statistical Methods

All statistical analyses for HAI (or MN) titers will be performed on the logarithmically transformed (base 10) values. Individual HAI titers below the detection limit (<10) will be set to half of that limit (5). Individual MN titers below the lower limit of quantification (LLOQ), will be set to half of that limit (1/2* LLOQ).

Unadjusted for GMT, GMRs and pertaining two-sided 95% CIs will be calculated assuming log-normal distribution of the titers and will be completed by providing minimum, maximum and median titers for each vaccine group.

Binary data (i.e. percentages of subjects with seroconversion and with titer $\geq 1:40$) will be summarized for each group using crude estimates and will be reported together with 2-sided exact 95% CIs. No multiplicity adjustment to the CI levels will be implemented.

For immunogenicity data, it may be reasonable to consider missing immunogenicity values as missing completely at random (MCAR), i.e. not informative. Therefore, the key secondary analysis will comprise a complete case analysis only, without introducing any bias. Imputation methods will not be used.

Further details of the statistical methods will be provided in the SAP.

8.4.4 Analysis of Exploratory Objectives

8.4.4.1 Analysis of Exploratory Safety Objectives

Not applicable.

8.4.4.2 Analysis of Exploratory Efficacy Objectives

Not applicable.

8.4.4.3 Analysis of Exploratory Immunogenicity Objectives

Exploratory immunogenicity endpoints of homologous CMI responses will be summarized using descriptive statistics by treatment group.

In case of additional exploratory immunogenicity analyses, the immune response will be further characterized similar to the analysis of secondary immunogenicity endpoints.

8.5 Sample Size and Power Considerations

QIVc will be tested against comparator, i.e. US-licensed comparator QIV. The treatment randomization ratio is 2:1 (Seqirus QIVc: Comparator QIV). This study is designed to achieve at least 90% power to demonstrate noninferiority for all of the 8 endpoints: seroconversion rates for 4 strains and GMT for 4 strains using a one-sided alpha of 0.025 for each comparison. No alpha adjustment for multiple endpoints will be made.

For comparisons of SCR a noninferiority margin of 10% (Comparator QIV-Seqirus QIVc) will be employed. It is assumed that the SCRs for A/H1N1, B strains and A/H3N2 based on TIVc are 81%, 69% and 85% respectively. These estimates are based on the estimated SCR rates of historical data, namely from study V58P16.

It is also assumed that the expected difference between antibody titers (QIV minus QIVc) is consistent with the SCR differences reported as per V58P16, namely 7% for A/H1N1 and 5% for A/H3N2 (based on the MN assay).

It is assumed there is no difference between Seqirus QIVc and the comparator QIV for the B/strain.

For comparison of GMT ratio a noninferiority margin of 1.5 (Comparator QIV/ Seqirus QIVc, equivalent to a difference on the log scale of 0.405465108) will be employed for the assessment of the A/H1N1, A/H3N2 and B strains. It is assumed that the GMT ratio's for A/H1N1, A/H3N2 and B strains for QIVc are 1.49 for the A/H1N1, 1.00 for the A/H3N2 (based on the MN Assay) and 0.84 for the B-strain. These GMT ratio estimates are consistent to those observed from protocol V58P16. It is assumed that the standard deviation of log (titer) is 1.3 across all strains.

Under these assumptions and with n evaluable = 1450 in the Seqirus QIVc group and 725 in the Comparator QIV the power for 4 GMT ratio endpoints is 94.90% and the power for 4 SCR endpoints is 99.40%. The overall global power of the 8 endpoints is then $94.90\% * 99.40\% = 94.33\%$. This provides a total N evaluable = 2175. Allowing for a 10% drop-out, 2418 subjects will be recruited for immunogenicity assessment. Approximately 84 additional subjects between 24 through 47 months of age will be enrolled to study CMI response, in order to have approximately 50 and 25 evaluable subjects in the QIVc

and Comparator QIV groups, respectively. Thus, approximately 2502 subjects will be enrolled in this study.

Sample size calculations were performed using PASS v12.0.02.

Table 8.5-1 summarizes the list of all co-primary endpoints with strains, the planned noninferiority margin and underlying assumptions used for the sample size computations.

Table 8.5-1 Summary of Assumptions Used for Sample Size Calculations

NI comparison	A/H1N1	A/H3N2	B strains
Test significance level, alpha (1-sided)	2.50%	2.50%	2.50%
Noninferiority Margin for the SCR comparison (%)	10	10	10
Assumed true SCR	81%	85%	69%
Power for SCR comparison tests for each strain (%)	100%	100%	99.7%
Global Power for 4 SCR Endpoints	99.40%		
Noninferiority Margin for the GMT ratio	1.5	1.5	1.5
Common Standard Deviation of \log_e (titer)	1.3	1.3	1.3
Power for GMT ratio tests for each strain (%)	100%	100%	97.42%
Global Power for 4 GMT ratio Endpoints	94.90%		
Global Power for 8 Co-primary Endpoints	94.33%		

Abbreviations: GMT = geometric mean titer; NI = noninferiority; SCR = serconversion rate.

Sample size calculations were performed using PASS v12.0.02.

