Statistical Considerations for Sample Size Calculations

QIVc will be tested against comparator, ie, US-licensed comparator QIV. The treatment randomization ratio is 2:1 (Seqirus QIVc: Comparator QIV). This study is designed to achieve at least 90% power to demonstrate noninferiority for all of the 8 endpoints: seroconversion rates for 4 strains and GMT ratios for 4 strains using a one-sided alpha of 0.025 for each comparison. No alpha adjustment for multiple endpoints needs to be made.

For comparisons of SCRs, a noninferiority margin of 10% (Comparator QIV-Seqirus QIVc) will be employed. It is assumed that the SCRs for A/ H1N1, B strains, and A/H3N2 based on TIVc are 81%, 69% and 85%, respectively. These estimates are based on the historical data, namely from study V58P16.

It is also assumed that the expected differences between antibody titers (QIVc minus QIV) are consistent with the SCR differences reported as per V58P16, namely 7% for A/H1N1 and 5% for A/H3N2 (based on the MN assay). It is assumed there is no difference between Seqirus QIVc and the comparator QIV for the B strain.

For comparison of GMT ratios, a noninferiority margin of 1.5 (Comparator QIV/ Seqirus QIVc, equivalent to a difference on the log scale of 0.405465108) will be employed. It is assumed that the GMT ratios for A/ H1N1, A/ H3N2, and B strains for QIVc/QIV are 1.49 for the A/H1N1, 1.00 for the A/H3N2 (based on the MN Assay), and 0.84 for the B strains. These GMT ratio estimates are consistent with those observed in study V58P16. It is assumed that the standard deviation of log (titer) is 1.3.

Under these assumptions and with n evaluable = 1450 in the Seqirus QIVc group and 725 in the Comparator QIV the power for 4 GMT ratio endpoints is 94.90 % and the power for 4 SCR endpoints is 99.40%. The overall global power of the 8 endpoints is then $94.90\% * 99.40\% = 94.33\%$. This provides a total N evaluable = 2175. Allowing for a 10% drop-out, $N=2418$ subjects will be recruited for immunogenicity evaluation.

Approximately 84 additional subjects between 24 through 47 months of age, in order to have approximately 50 evaluable subjects who received QIVc and approximately 25 evaluable subjects who received US-licensed QIV, will be enrolled to assess CMI response. Thus, a total of approximately 2502 subjects will be enrolled in this study.

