2.3 Sample Size and Power

Seqirus QIVc will be tested against comparator, i.e. US-licensed comparator QIV. The treatment randomization ratio is 2:1 (Seqirus QIVc: Comparator QIV).

This study is designed to achieve at least 90% power to demonstrate noninferiority for all of the 8 endpoints: seroconversion rates for 4 strains and Geometric Mean Titers (GMTs) for 4 strains using a one-sided alpha of 0.025 for each comparison. No alpha adjustment for multiple endpoints will be made. For comparisons of Seroconversion rate (SCR) a noninferiority margin of 10% (Comparator QIV-Seqirus QIVc) will be employed. It is assumed that the SCRs for A/H1N1, B strains and A/H3N2 based on Cell-based Trivalent Influenza Vaccine (TIVc) are 81%, 69% and 85% respectively. These estimates are based on the estimated SCR rates of historical data, namely from study *V58P16*.

It is also assumed that the expected difference between antibody titers (QIV minus QIVc) is consistent with the SCR differences reported as per *V58P16*, namely 7% for A/H1N1 and 5% for A/H3N2 (based on the MN assay).

It is assumed that there is no difference between Seqirus QIVc and the comparator QIV for the B/strain.

For comparison of GMT ratio, a noninferiority margin of 1.5 (Comparator QIV/ Seqirus QIVc, equivalent to a difference on the log scale of 0.405465108) will be employed for the assessment for the A/H1N1, A/H3N2 and B strains. It is assumed that the GMT ratios for A/H1N1, A/H3N2 and B strains for QIVc are 1.49 for the A/H1N1, 1.00 for the A/H3N2 (based on the MN assay) and 0.84 for the B-strains. These GMT ratio estimates are consistent to those observed from protocol *V58P16*. It is assumed that the standard deviation of $\log_e(\text{titer})$ is 1.3 across all strains.

Under these assumptions and with n evaluable = 1450 in the Seqirus QIVc group and 725 in the Comparator QIV the power for 4 GMT ratio endpoints is 94.90% and the power for 4 SCR endpoints is 99.40%. The overall global power of the 8 endpoints is then $94.9\% \times 99.4\% = 94.33\%$.

This provides a total N evaluable = 2175. Allowing for a 10% drop-out, 2418 subjects will be recruited for immunogenicity assessment. Approximately 84 additional subjects between 24 through 47 months of age will be enrolled to study CMI

Statistical Analysis Plan

Sponsor Name: Seqirus
Sponsor Protocol ID: V130_10

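### The 94.33% global power pairs a B-strain titer ratio of 0.84 with equal B-strain seroconversion; the zero is unsupported, and the 90% target is not secure above a deficit of about 2 points

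*Protocol*

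**What the plan says.** The power claim in Protocol 8.5 is "This study is designed to achieve at least 90% power to demonstrate noninferiority for all of the 8 endpoints", tested "using a one-sided alpha of 0.025 for each comparison". Evaluable numbers are 1450 QIVc and 725 comparator, the SCR margin is 10 points, the GMT-ratio margin is 1.5 and the SD of log titer is 1.3.

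The strain assumptions come in two sets:

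- **GMT ratios (QIVc/QIV).** The synopsis gives 1.49 for A/H1N1 and then "1.00 for the A/H3N2 (based on the MN Assay), and 0.84 for the B strains". The ratios are described as consistent with study V58P16.
- **SCRs.** The rates are 81% (A/H1N1), 85% (A/H3N2) and 69% (B), based on the cell-derived trivalent vaccine in V58P16. The A-strain differences are also attributed to V58P16, "namely 7% for A/H1N1 and 5% for A/H3N2 (based on the MN assay"). For B, Protocol 8.5 says "It is assumed there is no difference between Seqirus QIVc and the comparator QIV for the B/strain", and SAP 2.3 repeats it: "It is assumed that there is no difference between Seqirus QIVc and the comparator QIV for the B/strain". No source is cited for that sentence.

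Table 8.5-1 gives 100% power for both A strains on both endpoints. For the B strains it gives 99.7% (SCR) and 97.42% (GMT) per strain. The four-endpoint powers are 99.40% and 94.90%, and the row "Global Power for 8 Co-primary Endpoints" shows 94.33%. No sensitivity calculation appears in either document.

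**The concern.** Seroconversion is a threshold on the post-vaccination titer (for children below 1:10 at baseline) or on the fold rise (for the others). In randomized arms with similar baselines, lowering B-strain titers by 16% would ordinarily lower the share of children who cross either threshold. The plan lets the titer deficit reduce the GMT power but lets none of it reach the SCR power for the same strains.

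This matters because all eight tests must succeed and the A strains are shown at 100%. All the stated risk therefore sits in the two B strains, and the B-strain SCR power is very sensitive to small deficits. A reader relying on 94.33% would not know that it depends on an unsourced zero.

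**Working it through.** **Inputs (Protocol 8.5 and Table 8.5-1, same in SAP 2.3).** n = 1450 and 725; one-sided alpha 0.025 (critical value 1.96); SCR margin 0.10; B-strain QIVc rate 0.69; GMT margin 1.5; B-strain ratio 0.84; SD 1.3; powers combined by multiplication.

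**Step 1: reproduce the plan.**

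GMT, per B strain: the distance to the margin is ln 1.5 + ln 0.84 = 0.4055 − 0.1744 = 0.2311. The standard error is 1.3 × √(1/1450 + 1/725) = 0.0591. Power = Φ(0.2311/0.0591 − 1.96) = 97.43% (stated 97.42%). Squared: 94.93% (stated 94.90%).

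SCR, per B strain, with d the comparator rate minus the QIVc rate:

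Power(d) = Φ( (0.10 − d) / √(0.69 × 0.31/1450 + (0.69 + d)(0.31 − d)/725) − 1.96 )

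At d = 0 the standard error is 0.02104, so power = Φ(4.754 − 1.96) = 99.74% (stated 99.7%). Squared: 99.48%; the plan's 99.40% is 0.997². The global product is 94.4% (stated 94.33%).

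The figures reproduce with 0.84 in the GMT part and 69% against 69% in the SCR part.

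**Step 2: what deficit does 0.84 imply?** Treat log response as normal, with the comparator shifted up by ln(1/0.84) = 0.1744:

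comparator SCR = Φ(Φ⁻¹(0.69) + 0.1744/SD), where Φ⁻¹(0.69) = 0.4959.

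- SD 1.3, as in the GMT test: Φ(0.6300) = 73.6%, a deficit of 4.6 points. If 69% is taken as the comparator rate instead, the deficit is 4.9 points.
- SD calibrated to the plan's A/H1N1 pair (ratio 1.49; 81% against 74%, using the synopsis direction in which QIVc is higher): ln 1.49 / (0.8779 − 0.6433) = 0.3988/0.2346 = 1.70. The B-strain deficit is then 3.5 points.

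**Step 3: power by deficit.** This step needs no link model, only the plan's inputs and product rule.

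| B-strain SCR deficit (points) | Power per B strain | Four SCR tests | All eight tests |
|---|---|---|---|
| 0 | 99.7% | 99.5% | 94.4% |
| 1 | 99.1% | 98.1% | 93.1% |
| 2 | 97.1% | 94.2% | 89.4% |
| 3 | 92.4% | 85.4% | 81.1% |
| 4 | 83.4% | 69.6% | 66.0% |
| 5 | 69.2% | 47.9% | 45.4% |

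Break-even for 90% is a deficit of about 1.9 points. The two linked deficits of step 2 give 54.8% (4.6 points) and 74.1% (3.5 points).

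**Step 4: relax the product rule.**

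- *At 2 points:* an assumed GMT–SCR correlation of 0.5 within strain gives 90.3%, and 0.7 gives 91.1%. If covariates explain an assumed 10% of titer variance, the product is 91.3%; with correlation 0.5 as well, 92.0%.
- *At 3 points:* within-strain correlations up to 0.9, with or without the 10% covariate gain, give 81% to 85%. Adding a correlation of 0.9 between the two B strains, with 0.76 within strain, gives 88.8%. Only near-perfect correlation among all four B tests would pass 90%, since the ceiling is the single-test 92.4%.
- *At 4 points:* the ceiling itself is 83.4%.

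**The case against.** The strongest reply has four parts.

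**The arithmetic is right and the assumption is disclosed.** This stands. The plan states its powers under its listed assumptions, and they reproduce. A reader might infer a calculation error, but there is none. The weakness is in one input.

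**The historical B-strain SCR difference is unknown.** This stands. A reader might infer that V58P16 reported a deficit and that the plan replaced it with zero. The documents do not say so. They say only that zero is assumed, and the observed difference could have been zero or even in favour of QIVc.

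**The titer–SCR link is not exact.** This stands as a limit on size. The A/H3N2 pair (ratio 1.00, 5 points) departs from a pure shift, which would predict no difference. With SD 1.3 the link predicts 9.4 points for A/H1N1 against the plan's 7. Fitting both A pairs on the probit scale with an intercept gives a shift of 0.1948 + 0.0997 × ln 0.84 = 0.1774, which puts B-strain SCR about 6.5 points in favour of QIVc. Two pairs from different assays cannot identify a link, so that figure is no more reliable, but it shows that the A-strain data do not settle the sign. Moreover, 1.3 is the SD of log titer; the SD of the fold rise, which governs seroconversion in children with baseline antibody, is not given. Hence 55% and 74% illustrate particular models. A reader might infer that global power is below 90%; the documents do not establish that.

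**The product rule is conservative.** This stands near 2 points, as step 4 shows, but does not rescue a deficit of 3 points under realistic correlations.

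What the reply does not supply is a reason for combining 0.84 with zero. The GMT power already relies on a log-normal shift with a common SD, and under that model equal seroconversion is not the expected result.

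**Conclusion.** The concern holds as a conditional one. The 99.40% and 94.33% are correct for their inputs, but the B-strain inputs are not coherent with each other, and the zero has neither source nor justification.

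Under the plan's product rule, the 90% claim holds up to a B-strain SCR deficit of about 1.9 points, is borderline at 2 points (89% to 92% depending on correlation and covariate gain) and fails at 3 points or more. The deficit implied by 0.84 is about 4 to 5 points under the GMT test's own model, or 3.5 points if calibrated to A/H1N1. Whether such a deficit exists cannot be told from the documents.

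The A strains are kept at 100%, which requires the synopsis direction for their SCR differences (QIVc higher). Protocol 8.5 and SAP 2.3 print the opposite sign, and those passages should be reconciled. The B-strain result does not depend on that sign, apart from the A/H1N1 calibration. Only power is affected; type I error, margins and success criteria are not.

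**What to change.** In Protocol 8.5, Table 8.5-1, the synopsis and SAP 2.3:

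1. State the B-strain SCR difference observed in V58P16, the study that supplied 0.84. If zero is kept, give the reason it is compatible with 0.84.
2. Restate the B-strain SCR power and the four- and eight-endpoint global powers with B-strain inputs that fit together.
3. Show those powers for B-strain SCR deficits of 0 to 5 points, and say whether the tests are treated as independent.

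The cost is a re-run of an existing calculation and possibly a less favourable stated power. Sample size, margins, endpoints and analyses do not change, and no subjects are added.
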